1.5 SIGNIFICANCE

Early whole blood resuscitation has significant potential to prevent downstream manifestations of shock and coagulopathy, attenuate glycocalyx injury, improve microcirculatory hemodynamics and provide the most hemostatic and definitive resuscitation available.^{24,35,42,43} It is the ability to initiate needed whole blood in the prehospital setting to those patients who would benefit most, at the earliest time post-injury, before hemorrhagic shock and coagulopathy can result in their detrimental consequences, which underscores the significance of the impact of the study.

The University of Pittsburgh, Presbyterian Hospital has over the last 2 years initiated an urgent release whole blood transfusion program for trauma patients in hemorrhagic shock in our emergency department utilizing LTLR-WB identical to the proposed intervention for the pilot and large multicenter trial. We published data on the first 47 patients demonstrating the feasibility and initial safety of such a program.²⁸ We have continued this program and have currently utilized LTLR-WB in over 187 patients with no safety concerns. We have simultaneously been monitoring LTLR-WB patients for hemolytic side effects from ABO mismatched whole blood.²⁹ In 27 non-group O patients, there were no significant differences in laboratory hemolysis markers. These preliminary and published data verify the feasibility and safety of this type of intervention in patients with hemorrhagic shock, providing the backdrop for the successful execution of the proposed pilot trial and future large multicenter trial.

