2.3 STUDY INTERVENTION

The study intervention will be the initiation of prehospital through in-hospital transfusion of LTLR-WB in patients meeting all inclusion and no exclusion criteria. Whole blood units will be obtained from a local FDA licensed blood center (LifeSource dba Central Blood Bank; Registration number: 2571073; License number: 1025).

Up to two units of LTLR-WB (O+) will be initiated in the prehospital phase of the study with an additional 6 units of LTLR-WB (O+) available during the in-hospital phase of the trial if indicated.

Study Intervention Rationale: To provide the earliest and most robust intervention with appropriate concern for blood banking resource utilization, a prehospital and in-hospital phase intervention will be utilized. As whole blood resuscitation is most pertinent to patients with acute hemorrhage, we have limited the in-hospital acute resuscitation phase time period and the additional 6 units of LTLR-WB to 4 hours post-admission. This acute phase resuscitation period definition is based upon unpublished data from the recently completed PAMPer study at our institution.⁴⁰ Over 79% of the blood products transfused in the first 24 hours occurred in the first 4 hours following admission.

Whole Blood Intervention: Blood from male only, group O+ donors will be collected using the FDA approved Terumo Imuflex® WB-SP blood bag system. With this collection system, whole

blood passes through a platelet sparing inline leukoreduction filter into a bag containing citrate phosphate dextrose solution. Male only whole blood donors will be used in order to mitigate the risk of transfusion related acute lung injury (TRALI; estimated incidence ≈1:12,000). Whole blood collected with this system can be kept as such for up to 21 days when stored between 1-6°C. Per blood bank protocol, the anti-A and anti-B antibody titers in each unit will be tested on a sample from every donor using an immediate spin saline tube method without incubation; only units where the titer of both anti-A and anti-B are <100 will be issued for the study and subsequent transfusion. All other required transmissible disease testing will also be performed on these LTLR-WB units before they are released, as per blood bank standard practice. The LTLR-WB units will have affixed on them the standardized Whole Blood product label thereby making them easily distinguishable from the other non-WB units in inventory.

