2.4 INTERVENTIONAL ARM

Prehospital Phase Interventional Arm: Two units of LTLR-WB (O+) will be stored at each helicopter base in temperature regulated blood bank approved refrigerators for up to 14 days, which is the period within which cold stored platelets are thought to retain maximal function. Two units of LTLR-WB will be transported on all air medical flights with prehospital staff in blood banking approved and verified coolers. The temperature of the blood will be monitored throughout transit and storage in accordance with standard blood banking and Stat MedEvac procedures. Following 14 days without use, LTLR-WB will be replaced with new LTLR-WB units and the old products will be returned to the blood bank for recycling into PRBCs.. During transport, storage and during all flights standard STAT MEDEVAC protocols for storing and carrying blood products at the base and on the helicopters will be followed. While at the bases the blood units are stored in a dedicated blood refrigerator and moved to cooler for transport only when the aircraft is launched. The blood is packaged in the coolers with a thermometer for temperature maintenance to assure that they are maintained at 2-5 degrees Celsius at all times. The Clinical Protocol that is currently followed and will be followed for all blood products in the study can be found in Appendix 1. Our FDA approved blood bank will follow all regulations required by the FDA for safe blood and blood component transfusion. On day 15, after ensuring the WB unit had remained in temperature compliance and is otherwise eligible for recycling according to 21 CFR 640.2(c), the WB unit will be recycled into a PRBC unit following the standard operating procedures at the Centralized Transfusion Service in Pittsburgh.

Patients who meet all inclusion and no exclusion criteria at the scene, at a referral hospital or during transport and are randomized to the interventional arm will receive up to 2 units of LTLR-WB (O+) en-route to a PPOWER participating trauma center based upon hemodynamic status using identical criteria as the Prehospital Standard of Care arm. If the intervention is completed during transport, standard operating procedures for the prehospital setting will be employed by the prehospital providers during the remaining flight. (Appendix 7)

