lactate and shock index (SI, heart rate/systolic blood pressure-bpm/mmHg) 4) Acute Respiratory Distress Syndrome (ARDS): We will compare pulmonary dysfunction using the Berlin definition for ARDS.⁸⁶ 5) Nosocomial Infection (NI): We will compare the incidence of pneumonia and blood stream infections. 6) Mortality: We will compare mortality rates at 3, 6 and 24 hours following arrival, all cause in-hospital and 28-day mortality. 7) Blood component transfusion and resuscitation requirements at 24 hours: We will compare overall blood component transfusion requirements and crystalloid/colloid resuscitation requirements across the two arms. 8) Acute Hemolytic Transfusion Reaction (AHTR): We will compare the incidence of AHTRs across study arms as defined by the CDC/National Healthcare Safety Network (NHSN) Hemovigilance Surveillance definition. (www.cdc.gov/nhsn) Length of hospital stay and intensive care unit stay. Length of stay and ICU resources will be descriptively compared. Patients will be followed for 28 days from admission for the 28-day mortality outcome utilizing chart review, patient contact or utilization of the social security death index for those who cannot be contacted.

Predefined Subgroup Analyses: Predefined subset analyses for the pilot trial will be performed looking at our primary outcomes (safety/efficacy and feasibility) in 1) Females > 50 years of age versus study cohort with females < 50 years excluded ; 2) Patients who ultimately did or did not require in-hospital blood transfusion; 3) Patients with and without significant traumatic brain injury (Head abbreviated injury score- AIS >2); 4) Patients enrolled from the scene of injury versus those enrolled from a referral hospital; 5) Patients that require operative intervention in the first 24 hours; 6) Those patients with a preinjury history of anticoagulation / antiplatelet therapy; 7) Patients who ultimately did or did not require massive transfusion (≥ 10 units blood in first 24 hrs) 8)Patients who did or did not receive prehospital PRBCs.

Clinical Outcome Definitions:

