Multiple Organ Failure (MOF): Organ dysfunction will be evaluated via the Denver Post-injury Multiple Organ Failure Score, a well-validated scoring system in injured patients and characterized as an incidence rate (%) and as MOF free days.^{84,87} Patients who are never admitted to the ICU or those with a length of ICU stay of less than 48 hrs will be considered to have a Denver score of 0. A summary of the Denver score may be calculated by summing the worst scores of each of the individual systems over the course of the ICU stay. A summary Denver score > 3 will be classified as MOF. Scores will be determined daily up until ICU discharge.⁸⁷ Mean Denver Post-injury MOF Score: As the primary endpoint for the pilot trial, the 3 highest (worst) daily Denver scores will be averaged and compared across the treatment arms. Patient not in the ICU will be given a score of 0. Acute Respiratory Distress Syndrome (ARDS): The Berlin definition for mild ARDS (PaO_2/FIO_2 , ≤ 300 mm Hg + timing, imaging and origin criteria) will be utilized as a threshold value to determine the incidence of ARDS and will be further stratified into Moderate (PaO_2/FIO_2 , ≤ 200) and Severe (PaO_2/FIO_2 , \leq 100).⁸⁶(Nosocomial Infection (NI): The CDC criteria for the diagnosis of hospital acquired pneumonia and blood stream infection will be utilized (www.cdc.gov/nhsn) Mortality: We will derive the time to a mortality event from the time of admission for 6 hour and 24 hour mortality rates over the initial 24 hours. All cause in-hospital and 28-day mortality will be similarly determined from the date of admission. 7) Blood component transfusion and resuscitation requirements at 24 hours: Blood component transfusion needs per unit (PRBC, FFP, PLT) will be recorded over the first 24 hours of admission with 6-hour incremental totals. For every unit of LTLR-WB that is transfused each will be designated as 1 unit of PRBC, 1u of FFP and a single pack of platelets. Similar recording of crystalloid volume and colloid volume of the initial 24 hours following admission will be undertaken. 8) Acute Hemolytic Transfusion Reactions: We will compare the incidence AHTRs (CDC NHSN Hemovigilance Surveillance definition) and will measure arrival serum haptoglobin levels. 9) Length of hospital and intensive care unit (ICU) stay: Length of stay will be determined from the date of admission for all enrolled patients.

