2.9 STATISTICAL ANALYSIS

The overarching goals for the pilot trial are to evaluate safety, efficacy and feasibility of a LTLR-WB prehospital through in-hospital protocol to plan for the successful execution of a large, multicenter clinical trial. All analyses will be performed based on the intent-to-treat principle for the prehospital randomization and analyses will include all enrolled patients grouped by randomization assignment. This pilot study will guide the calculation needed for the large, multicenter clinical trial and will provide estimation for intra-cluster correlation coefficient and sample size variation across clusters. We will report 95% confidence intervals for all measurements

Safety and Efficacy Analysis: 28-day mortality is the primary safety and efficacy outcome and will be compared across randomized groups. Utilizing intention to treat principles we will compare the LTLR-WB and Standard of Care arms using a pooled Z test for comparing two independent proportions. We will additionally perform survival analysis for all mortality outcomes including 3hr, 6hr, 24hr, and 28day time points across the two arms of the study testing the differences using log rank test.

Eligibility, Enrollment, and Subject Accrual Anlaysis: The feasibility of enrollment will be evaluated by determining 1) the number of patients that meet the eligibility criteria for the trial; 2) the proportion of eligible patients that can be randomized and 3) the proportion of eligible patients who are enrolled in the trial. These proportions will be estimated directly as the observed ratio of numbers of patients, and 95% confidence intervals will be calculated to understand the likely range of values for a larger study with a comparable research protocol. The reasons why patients are not enrolled including frequencies of individual exclusions and the proportion of patients declining participation or not able to be randomized will be described. Rate of subjects' accrual per month with 95% C.I. will be calculated.

Adherence and Minimization of Bias: Adherence rates for each treatment arm of the protocol will be ascertained as the proportion of enrolled patients who adhere to the intervention (LTLR-WB vs. standard care) as assigned. Estimated proportions and 95% confidence intervals will be created. The trial has been designed to negate intervention arm crossover and maximize follow-up completion.

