6. POTENTIAL RISKS AND BENEFITS

6.1 POTENTIAL RISKS

Risks Associated With LTLR-WB: The whole blood product to be utilized starting in the prehospital environment in the pilot clinical trial is the identical product to be used in the hospital and identical to the current whole blood product that has been transfused in over 200 patients over the last 24 months at the University of Pittsburgh without evidence of complications or transfusion reactions. The primary risk with LTLR-WB is a hemolytic transfusion reaction which will be followed as an important secondary outcome. There have been no hemolytic transfusion reactions in over 200 patients transfused LTLR-WB at the University of Pittsburgh in the last 24 months. The primary risks with any blood transfusion can be found in the Circular of Information prepared jointly by AABB, the American Red Cross, America's Blood Centers, and the Armed Services Blood Program. Those primary acute immunologic complications include hemolytic transfusion reactions, immune mediated platelet destruction, febrile nonhemolytic reactions, allergic reactions, anaphylactoid reactions and transfusion-related acute lung injury (TRALI). Delayed immunologic complications include delayed hemolytic reaction, alloimmunization, posttransfusion purpura, transfusion-associated graft-vs-host disease. Nonimmunologic complications include transmission of infectious agents, bacterial sepsis, transfusion-associated circulatory overload (TACO), hypothermia and metabolic complications.

The primary risk associated with transfusion of Rh+ blood into a woman of child-bearing potential (WCP) is hemolytic disease of the fetus and newborn (HDFN) of a future pregnancy. Complications of HDFN include fetal anemia, fetal hydrops, and in the most severe cases, fetal death. However, the overall risk of poor fetal outcome in a future pregnancy for Rh- women that are administered Rh+ blood products has been estimated to be less than 0.5%⁹⁰. Of note, the incidence of a female being Rh- is only 15%. This means that the majority of WCP are at no risk of Rh mismatch. For those WCP that are at risk, the likelihood of poor fetal outcome is very small.

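### Acute hemolytic reactions, the named primary risk of whole blood, have no analysis in patients who received it and no split by recipient ABO group

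*Combined protocol and SAP*

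**What the plan says.** Section 6.1 sets the importance of the endpoint: "The primary risk with LTLR-WB is a hemolytic transfusion reaction which will be followed as an important secondary outcome". Section 2.8 lists it as secondary outcome 8, "We will compare the incidence of AHTRs across study arms", and repeats it among the outcome definitions: "We will compare the incidence AHTRs (CDC NHSN Hemovigilance Surveillance definition) and will measure arrival serum haptoglobin levels". Neither item, nor the AHTR lines in Section 2.9, nor the hemolytic reaction row of Table 4 (Appendix 8), states who is in the denominator.

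The only denominator comes from the opening paragraph of Section 2.9, which puts all analyses under intention to treat and adds that "analyses will include all enrolled patients grouped by randomization assignment". Section 2.9 also plans a proportion and 95% interval for each outcome over both arms combined.

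Exposure is conditional. Before arrival, intervention-arm patients "will receive up to 2 units of LTLR-WB (O+) en-route", depending on hemodynamic status (Section 2.4). In hospital, up to six further units are given if blood products are required. Section 5.1 lets patients missed by the flight crew be enrolled in the emergency department and analysed in their arm of origin.

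On the product, Section 2.3 states that "only units where the titer of both anti-A and anti-B are <100 will be issued for the study". On the site's earlier experience, Section 1.5 reports: "In 27 non-group O patients, there were no significant differences in laboratory hemolysis markers".

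**The concern.** An all-enrolled denominator answers whether assignment to LTLR-WB changes the AHTR rate. It does not answer how often the product causes hemolysis in a patient who receives it and whose red cells carry the A or B antigen. A patient assigned to LTLR-WB who receives none counts as exposed and reaction-free. A group O recipient cannot show the anti-A or anti-B reaction that the titer limit is meant to prevent.

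Nothing else in the plan fills the gap. There is no safety or as-treated population. The subgroup defined by in-hospital transfusion in Section 2.8 covers the primary outcomes only and ignores prehospital units. Recipient ABO group appears neither in the data items of Section 6.5.1 nor in Table 1.

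Safety is a principal objective of the pilot, and Section 2.9 says the intervals serve safety and the planning of the larger trial. With few or no AHTRs expected, the upper confidence limit is most of what this endpoint can contribute.

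**Working it through.** **The plan's own figure.** None is given for AHTR. The only size figure is for mortality: 56 per arm, 33% versus 11%, two looks. It reproduces: drift = 0.22 / √(2 × 0.22 × 0.78 / 56) = 2.810, and power at the printed boundaries is 0.801. So 56 per arm is used below.

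**Inputs**
- Assigned to LTLR-WB: 56 (Section 2.9).
- Group O share: 37.4% + 6.6% = 44.0%, so non-O is 56.0%. Section 2.2 gives these as shares of the blood supply. That recipients resemble the supply is an assumption; 37% to 50% was also tried.
- Share of the LTLR-WB arm given at least one unit: not in the documents. Assumed 60% to 100%.

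**Formula.** For zero events in n patients, the exact (Clopper-Pearson) two-sided 95% upper limit is 1 − 0.025^(1/n). For one event the corresponding exact limit is used.

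**Patients at risk of anti-A/anti-B hemolysis**
- All transfused: 56 × 0.56 = 31.4, about 31.
- 80% transfused: 31.4 × 0.8 = 25.1, about 25.
- 60% transfused: 31.4 × 0.6 = 18.8, about 19.

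| Denominator | n | 0 events: upper limit | 1 event: rate (upper limit) |
|---|---|---|---|
| All enrolled, LTLR-WB arm | 56 | 6.4% | 1.8% (9.6%) |
| Non-O, all transfused | 31 | 11.2% | 3.2% (16.7%) |
| Non-O, 80% transfused | 25 | 13.7% | 4.0% (20.4%) |
| Non-O, 60% transfused | 19 | 17.6% | 5.3% (26.0%) |

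The one-event figures in the non-O rows suppose that the event occurs in an exposed non-O patient.

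**Sensitivity.** Over group O shares of 37% to 50% and transfused shares of 60% to 100%, the zero-event limit in exposed non-O patients runs from 10.0% to 19.5%.

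**Exposure alone.** Keeping all ABO groups but only transfused patients, the zero-event limit is 7.9% for 0/45 (80% transfused) and 10.3% for 0/34 (60%).

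**Both arms combined.** The combined estimate planned in Section 2.9 would give 3.2% for 0/112. Half of those patients are not assigned to the product.

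**The case against.** The strongest reply is that AHTR here is the national hemovigilance surveillance definition, which is not confined to donor anti-A or anti-B. Section 6.1 lists hemolytic reactions as a risk of any transfusion, and LTLR-WB is Rh-positive and given without typing or crossmatching. A reader might infer that group O recipients cannot react and that the headline interval should come from non-O recipients alone. The documents do not support that: such an interval would discard any AHTR in a group O patient. This part of the objection stands.

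Four further points stand in part.
- The all-enrolled denominator is inferred from the general rule. It is the only rule given, and nothing overrides it.
- With zero events the rate is 0% on any denominator, so only the upper limit moves.
- Receiving a unit is a post-randomisation event driven by hemodynamics and clinical judgement, so a transfused-only comparison is not randomised. Controls also receive uncrossmatched red cells and components.
- A reader might infer that a planned haptoglobin comparison is diluted by group O patients. The plan says only that arrival haptoglobin will be measured; it names no test, and Table 4 has no row for it.

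It can also be said that no decision hangs on the limit. The primary safety outcome is mortality, no AHTR threshold or stopping rule exists, suspected reactions are investigated individually, and the monitoring board is expected to review adverse events by arm every six months. That limits the consequence but does not make the all-enrolled figure an estimate of product risk. Section 6.1 itself reports the site's record of no hemolytic reactions per transfused patient (over 200), and Section 1.5 reports laboratory markers in non-O patients.

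**Conclusion.** The concern holds as a missing supplementary analysis, not as an error in the randomised comparison. If the plan is followed as written, the only AHTR interval for the LTLR-WB arm has an upper limit of 6.4% with no events. The figure for patients exposed to ABO-mismatched plasma is about 11.2% if all are transfused, and 13.7% if 80% are. With one event in such a patient, the all-enrolled rate is too low for that group by a factor of 1/0.56 = 1.8 if all are transfused, rising to 1/(0.56 × 0.6) = 3.0 if 60% are.

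These sizes rest on two assumptions: that recipients' blood groups resemble the supply, and the share transfused. The entry criteria select patients in shock, so the untransfused share may be small; the ABO part of the gap remains even if it is nil. The documents do not show that the larger trial would be decided differently on one limit or the other.

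**What to change.** Keep the intention-to-treat comparison by arm. In Section 2.8 item 8, Section 2.9 and Table 4, add:
- AHTR incidence with exact 95% limits among patients who received at least one LTLR-WB unit, prehospital or in-hospital. Show it for all ABO groups together, then for recipient group O and non-O separately.
- Matching figures for control patients who received any blood product.
- AHTRs per unit transfused. Count each LTLR-WB bag once, because Section 2.8 recodes each as three component units for the resuscitation totals.
- A label stating that these are descriptive estimates in an exposed population, not randomised contrasts.
- If arrival haptoglobin is compared by arm, the same split by recipient ABO group.

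Add recipient ABO group to the data items in Section 6.5.1. Units transfused are already recorded. The cost is one extra data field, a few table rows, and a wider, less favourable interval. Design, sample size and treatment are unchanged.

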1.2 SPECIFIC AIMS

Hypothesis: The initiation of LTLR-WB resuscitation in the prehospital setting with continuation through the in-hospital acute resuscitation phase of care will significantly reduce the morbidity and mortality attributable to hemorrhagic shock post-injury as compared to standard prehospital and in-hospital resuscitation practice.

Specific Aims:

Specific Aim I: Determine the feasibility and most appropriate study population that will lead to a large multicenter clinical trial designed to evaluate the effectiveness of prehospital through inhospital LTLR-WB as compared to standard care practice in patients at risk of hemorrhagic shock.

Specific Aim II: Determine if prehospital through in-hospital LTLR-WB reduces 28-day mortality, in-hospital mortality, multiple organ dysfunction, presenting coagulopathy, 24-hour resuscitation requirements and early mortality as compared to standard of care prehospital and in-hospital resuscitation in patients at risk of hemorrhagic shock.

Specific Aim III: Determine the primary drivers by which prehospital through in-hospital LTLR-WB improves clinical, resuscitative and hemostatic outcomes as compared to standard of care prehospital and in-hospital resuscitation in patients at risk of hemorrhagic shock.

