Estimates for Trial Secondary Clinical Outcomes: We will estimate the mean differences in the average Denver post-injury MOF score derived from the 3 highest daily scores between two treatment groups as the main clinical outcome for the pilot trial. We will also record and compare the overall proportion of patients who developed MOF based on Denver score > 3 and compare MOF free days. Similarly, the incidence of ARDS, NI, mortality (6hr, 24hr and 28 day) and hemolytic transfusion reactions will be recorded. We will perform survival analysis for all mortality outcomes. Blood component and resuscitation volumes over the initial 24 hours, length of ICU stay, days on a ventilator, and total hospital stay will be also be determined. Estimated proportions and means and 95% confidence intervals will be created for each outcome using the data from the entire pilot trial (i.e. combining the data from the two assigned treatment arms). Absolute and relative differences for continuous levels and event rates by assigned treatment will be estimated and 95% confidence intervals will be calculated to identify potential treatment differences for safety and for study planning purposes. Subgroup analyses will be exploratory and be based on baseline factors specified prior to the initiation of the trial.

The Following Outcomes Will Be Recorded:

- 1. The average Denver post-injury MOF score derived from the 3 highest daily scores. Differences between these averages will be estimated across the study two arms.
- Proportion of patients who developed MOF based on Denver score > 3 and compare MOF free days across the study two arms.
- 3. The incidence of ARDS, NI, mortality (6hr, 24hr and 28 day) and hemolytic transfusion reactions will be recorded and compared across the study two arms
- 4. Survival analysis in relation to all causes of death.
- 5. Blood component and resuscitation volumes over the initial 24 hours,
- 6. Length of ICU stay, days on a ventilator, and total hospital stay will be also be determined.

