Sample Size Justification for Pilot Trial: Assuming a baseline in-hospital mortality risk of 33% in the control arm as was demonstrated in the recently completed PAMPer trial with all cause in-hospital mortality as the primary outcome, enrolling **56 patients in each arm, 112 total patients** and using a 2 sided alpha of 0.05, the study will have a 80% power to detect a 22% (33% to 11%) or greater difference in in-hospital mortality. Based upon current PAMPer clinical outcome data and the additional benefit attributable to LTLR-WB when it is initiated in the prehospital setting, the current proposed mortality difference is clinically meaningful and of sufficient magnitude to influence clinical practice for a pilot trial. The above sample size will provide more than sufficient power for the originally planned feasibility outcomes as we have increased our sample size by 24%. The above power analysis was generated assuming 2 sequential tests using the O'Brien-Fleming spending function to determine test boundaries which are depicted in the following table and graph.

Details	Details when Spending = O'Brien-Fleming, N1 = 56, N2 =56, P1 = 0.1100, P2 = 0.3300							
		Lower	Upper	Nominal	Inc	Total	Inc	Total
Look	Time	Bndry	Bndry	Alpha	Alpha	Alpha	Power	Power
1	0.50	-2.96259	2.96259	0.003051	0.003051	0.003051	0.164669	0.164669
2	1.00	-1.96857	1.96857	0.049002	0.046949	0.050000	0.636252	0.800921
Drift 2.	81024							

Based upon the busy air medical service at the University of Pittsburgh, the bases to be utilized for the pilot trial, 61 patients who met all inclusion and exclusion criteria for the current proposed pilot trial, were admitted to Presbyterian Hospital, consented and were enrolled (www.pamperstudy.com) over a 12 month period 6/2015-5/2016. Based upon a planned enrollment period of 2.5 years, this sample size is feasible after accounting for consent rates and exclusions.

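### The subgroup plan never estimates how the treatment effect differs between levels, and three of its eight items, as worded, allow no valid contrast

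*Combined protocol and SAP*

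**What the plan says.** Section 2.8 (Predefined Subgroup Analyses) opens with "Predefined subset analyses for the pilot trial will be performed looking at our primary outcomes (safety/efficacy and feasibility) in" and lists eight items:

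- Item 1 sets women over 50 against the study cohort with younger women removed.
- Items 3 and 4 are two-level: head injury (head AIS above 2) yes or no, and scene v referral hospital.
- Item 5 names only patients operated on within 24 hours.
- Item 6 names only "Those patients with a preinjury history of anticoagulation / antiplatelet therapy".
- Items 2, 7 and 8 split patients by in-hospital transfusion, massive transfusion and prehospital red cells.

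Section 2.9 says: "Subgroup analyses will be exploratory and be based on baseline factors specified prior to the initiation of the trial". The sentence before it plans absolute and relative differences by arm with 95% confidence intervals, for safety and to help plan a later study. The pooled Z and log-rank tests in section 2.9 are named for the comparison of the randomized arms. Section 6.4.2 has the DSMB monitor outcomes in the a priori subgroups and gives no method. The Appendix 8 table shells contain no subgroup table. Aim I (section 1.2) seeks the "most appropriate study population that will lead to a large multicenter clinical trial".

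**The concern.** A subgroup analysis addresses whether the treatment effect depends on a patient characteristic. The quantity that answers this is the difference between the two arm effects, with its interval. The plan never asks for it. Without it, the reader has a set of subset results and will tend to note which intervals exclude no effect and which do not. That is not a comparison of effects: when each subset is small, one level often crosses the threshold and the other does not, even though treatment works equally in both.

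At stake is how the pilot's results are read when the larger trial is designed. Aim I concerns the population for that trial, and treatment differences are explicitly estimated for planning. Narrowing the population on such a pattern would rest on chance. The primary mortality comparison itself is not affected.

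**Working it through.** **Inputs (section 2.9).** Control risk: "Assuming a baseline in-hospital mortality risk of 33% in the control arm". Size: "56 patients in each arm, 112 total patients". Effect and alpha: "using a 2 sided alpha of 0.05, the study will have a 80% power to detect a 22% (33% to 11%) or greater". Monitoring: "assuming 2 sequential tests using the O'Brien-Fleming spending function to determine test boundaries". Test: pooled Z for two proportions. The 33% is an in-hospital figure; it is used here as the planning value for mortality.

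**The plan's own power.** Pooled drift = 0.22 / √(2 × 0.22 × 0.78 / 56) = 2.8102 (table: 2.81024). With boundaries ±2.96259 and ±1.96857, power is 0.1647 at the first look plus 0.6363 at the second, total 0.8010 (table: 0.800921). Alpha is 0.0500. The stated figure reproduces.

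**One subgroup, two equal halves.** This gives 28 per arm in each half. Assume the same true effect in both halves, independent patients, and a subgroup factor unrelated to risk. In the normal approximation, power in one half is

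Φ{(0.22 − 1.96 × √(2 × 0.22 × 0.78 / 28)) / √((0.33 × 0.67 + 0.11 × 0.89) / 28)} = Φ{(0.2200 − 0.2170) / 0.1067} = 0.511.

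Exact binomial enumeration of the pooled Z test gives 0.515. The chance that exactly one half is significant is 2p(1 − p) = 2 × 0.515 × 0.485 = 0.500. Both are significant with probability 0.515² = 0.265, and neither with 0.485² = 0.235.

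**Dependence on the true effect** (equal halves, control 33%):

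| Treated risk | Exact power per half | Exactly one half significant: exact (approximation) |
|---|---|---|
| 11% | 0.515 | 0.500 (0.500) |
| 15% | 0.347 | 0.453 (0.454) |
| 20% | 0.196 | 0.315 (0.311) |
| 25% | 0.103 | 0.185 (0.173) |
| 33% (no effect) | 0.052 | 0.099 (0.095) |

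**Unequal splits at 33% v 11%.** With powers p and q in the two levels, the chance is p(1 − q) + q(1 − p):

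- 20 and 36 per arm: 0.398 × 0.370 + 0.630 × 0.602 = 0.53
- 14 and 42 per arm: 0.286 × 0.290 + 0.710 × 0.714 = 0.59
- 11 and 45 per arm: 0.198 × 0.254 + 0.746 × 0.802 = 0.65

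**Clustering.** Assignment is by base and month, and no intra-cluster correlation is given. Dividing 28 by an assumed design effect of 1.1, 1.25, 1.5 or 2.0 gives 0.50, 0.49, 0.46 or 0.41 for equal halves at 33% v 11%.

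**What an interaction estimate would show.** For equal halves at 33% v 11%:

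- 95% half-width within one half: 1.96 × √(0.319 / 28) = 0.209, where 0.319 = 0.33 × 0.67 + 0.11 × 0.89.
- 95% half-width of the difference of risk differences: 1.96 × √(2 × 0.319 / 28) = 0.296.
- In 400,000 simulated trials with a uniform effect, the interaction test is falsely significant in 5.8% (Wald, risk differences) or 2.5% (log odds ratios).
- If the effect is 22 points in one half and zero in the other, the interaction test has about 28% power.

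**Which items can carry a contrast.** Items 3 and 4 are two-level and describe the patient or injury before treatment. Item 6 is a baseline factor but lacks its second level. Item 1 is a baseline factor, but women over 50 appear in both groups being compared. Items 2, 5, 7 and 8 depend on care or events after assignment. They therefore conflict with the baseline-factor statement in section 2.9, and item 5 also lacks a second level.

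**The case against.** The strongest reply is that the plan does not do what the arithmetic supposes. No section prescribes a significance test inside a subset. The text around the subgroup sentence in section 2.9 speaks of differences with 95% intervals, and the analyses are labelled exploratory. Items 1, 3 and 4 are worded as comparisons between groups. All of this stands, and it limits the consequence. It does not supply the missing quantity: two separate intervals, one excluding zero and one not, invite the same misreading.

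A reader might infer that the plan selects subsets by significance and so will misdirect the choice of population under Aim I. The documents do not support that. No section ties subgroup mortality results to that choice, and the feasibility outcomes in section 2.8 (eligibility, characteristics of those enrolled, outcome frequencies, base differences) offer another route to it. Section 6.4.2 gives the DSMB no subgroup decision rule.

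A reader might also compound the risk over all eight items. That would need eight independent, complementary splits unrelated to risk, and section 2.8 does not contain them: item 1 overlaps, items 5 and 6 are one-sided, and items 2, 7 and 8 all concern transfusion and are plausibly related to one another and to mortality.

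Finally, the interaction estimate will be too imprecise to settle anything. That is true, but printing the width tells the reader so.

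**Conclusion.** The gap holds: the plan contains no estimate of how the arm effect differs between subgroup levels, and items 1, 5 and 6 could not provide one as worded. If readers compare which level reaches significance, a uniform effect would appear in exactly one of two equal halves in about 50% of trials at the planned 33% v 11%. The 50% is tied to the 22-point design effect: it falls to about 31% at 33% v 20% and 18% at 33% v 25%, and is about 10% with no effect. It rises to 65% for an 11/45 split per arm at the design effect. These figures assume independent patients and a factor unrelated to risk.

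Severity is minor. The analyses are exploratory, the primary result is unaffected, and the harm depends on how results are read rather than on a stated decision rule. An interaction cannot repair items 2, 5, 7 and 8.

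**What to change.** In sections 2.8 and 2.9:

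- Confine effect comparisons to baseline subgroups: items 3, 4 and 6, and item 1 redefined as non-overlapping groups. Define both levels of each; for item 6, prior anticoagulant or antiplatelet use yes v no.
- For each, report the arm difference with 95% CI in both levels, and the arm-by-subgroup interaction (difference of risk differences) with 95% CI. Give no p-values within levels.
- Base any statement about differing effects for the next trial's population on the interaction estimate. State that this pilot cannot establish heterogeneity, with an interaction interval of about ±30 points at equal halves.
- Report items 2, 5, 7 and 8 as descriptive only, and say that they are not baseline factors.

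The cost is SAP wording and a subgroup table in Appendix 8 with an interaction column; no new data are needed. The downside is wide interaction intervals and fewer subgroup claims.
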